**3. Abstract:**

The primary purpose of our study is to conduct a pilot, practice-based intervention focused on increasing adherence to the 6As for youth ages 11 through 17 years. We also will incorporate AAP best practice recommendations to screen and counsel parents. The specific aims of this study are to: (1) Develop and deploy an electronic short screening tool for tobacco and nicotine product use into pediatric primary care workflow in conjunction with clinician and office staff training on the 6As and parent screening through the use of trained Clinical Practice Facilitators, clinician-engaged adaptations of the intervention to fit their practice workflow, and support for Maintenance of Certification (MOC) to engage pediatricians in implementing the best practices; (2) Gather pilot data about the effectiveness of the intervention on clinician adherence to best practices and changes in practice capacity for change, adaptive reserve, and clinician self-efficacy; and (3) Examine the congruence between documentation of the intervention in the EHR and youth report of the intervention.

#### 4. Background:

Cigarette smoking remains the most preventable cause of death in the US and contributes significantly to the occurrence of chronic conditions. *Adolescents are a particularly vulnerable and important group to target for tobacco cessation.* Progression from occasional to daily smoking almost always occurs by age 26, an event that substantially increases the risk for chronic disease in adulthood. Moreover, there has been rapid growth in electronic or e-cigarette use and other non-cigarette tobacco products among youth, which may further increase their risk for transitioning to cigarette use and the development of other addictions.

*Primary Care Providers (PCPs) play a critical role in tobacco-related disease screening, counseling, and early intervention among youth.* There is an evidence base demonstrating that PCP brief interventions contribute to overall tobacco cessation and reduction. Yet there are significant gaps in screening and management of risk factors, counseling about e-cigarettes, parental counseling, and follow-up interventions to reduce tobacco and e-cigarette use in primary care.

We are proposing a pilot study to increase PCP capacity to follow evidence-based guidelines for tobacco and nicotine product screening and intervention among youth ages 11 through 17. We selected the 6As intervention for two primary reasons. First, the American Academy of Pediatrics (AAP) and the U.S. Preventive Services Task Force recommend their use. Second, the 6As strategy has an evidence base demonstrating that physician screening, advice, and referrals are effective in contributing to tobacco cessation among adolescents. The 6As are: (1) “Anticipate” (future use), (2) “Ask” (about tobacco use), (3) “Advise” (advise the patient to quit using tobacco), (4) “Assess” (the patient’s readiness to quit using tobacco), (5) “Assist” (by setting a quit date, providing materials on quitting tobacco, providing tobacco cessation medications, and referring the patient for additional services and/or counseling), and (6) “Arrange” (by re-contacting the patient after their quit date and arranging a follow-up visit). Consistent with AAP recommendations, we will include screening for e-cigarette, cigars, chewing tobacco, and hookah use.

Despite national recommendations, compliance with the 6As and other PCP office-based best practices are low. The majority of pediatricians advise patients who smoke to quit (81%) but only one-third discuss cessation strategies, and less than 20% make referrals to the quitline or other cessation programs. Facilitators to carrying out the 6As and other best practices in primary care include: incorporation of cues into electronic health records (EHRs); use of short screening tools to identify those at risk for initiating tobacco use as well as current tobacco users; development of patient registries to track outcomes and to facilitate implementation of mHealth applications focused on tobacco cessation; and training of clinicians and office staff on cessation counseling.

The primary purpose of our study is to conduct a pilot, practice-based intervention focused on increasing adherence to the 6As for youth ages 11 through 17 years. We also will incorporate AAP best practice recommendations to screen and counsel parents.

Secondarily, we want to better understand the effects of the practice intervention on enhancing practice capacity to adopt and sustain new interventions in the future. The systematic uptake of evidence-based practices (EBP) into primary care is influenced by multiple organizational characteristics including practice leadership, ability to adopt new interventions (capacity for change) and sustain them (adaptive reserve); HIT availability, and clinician self-efficacy around the particular EBP. Therefore, we will measure practice characteristics including practice capacity for change, adaptive reserve, and HIT capabilities and clinician self-efficacy around the 6As at baseline and at 3 months post intervention.

## 5. Specific Aims:

**Aim 1:** Develop and deploy an electronic short screening tool for tobacco and nicotine product use into pediatric primary care workflow in conjunction with 1) clinician and office staff training on the 6As and parent screening through the use of trained Clinical Practice Facilitators (CPFs), 2) clinician-engaged adaptations of the intervention to fit their practice workflow, and 3) support for Maintenance of Certification (MOC) to engage pediatricians in implementing the best practices.

[figure not shown]
**Aim 2:** Gather pilot data about the effectiveness of the intervention on clinician adherence to best practices and changes in practice capacity for change, adaptive reserve, and clinician self-efficacy.

**Aim 3:** Examine the congruence between documentation of the intervention in the EHR and youth report of the intervention.

## 6. Research Plan

### 6.1 Conceptual Framework

The Consolidated Framework for Implementation Research (CFIR) is guiding our proposed project (Figure 1). The CFIR emphasizes the influence of internal organizational, clinician, patient, and external factors on the *implementation* of new interventions. We included the CFIR to guide our work because it (1) emphasizes stakeholder engagement to understand local priorities and practice workflow in order to select and adapt patient-centered outcomes research for particular settings; and (2) focuses on understanding and working within the context of internal organizational and individual (clinician) factors when implementing new interventions. This current project is focused on practice and clinician level interventions. Patient factors, such as sociodemographic characteristics, health status, impulsivity, and other factors are integral to tobacco and nicotine product cessation interventions and will be incorporated into future research. Figure 1 reflects our current focus on practice and clinician factors related to implementation of the 6As and recommended best practices related to tobacco and nicotine produce screening and counseling.

## 6.2 Methods

### 6.2.1 Study Design

This study will be implemented with a convenience sample of 4 pediatric primary care practices. Two will be randomly assigned to receive the intervention and two will serve as the comparison groups. Two of the practices will be located at UF Health in Gainesville and two will be located at UF Health in Jacksonville. The control group will provide their usual care related to tobacco and nicotine product use screening and cessation recommendations. The control group will be given the opportunity to participate in the intervention following study completion.

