D. Parent Brief Questionnaire (PBQ – Appendix D): The PBQ was developed using questions recommended by the American Academy of Pediatrics. Parents are one of the most important sources of a child's tobacco smoke exposure. Therefore screening parents is a recommended best practice. The PBQ will also be administered using ResearchACTS.

E. 6As and Best Practices Medical Record Review Form (6As MRR - Appendix E): At baseline, we will request the (Medical Record Number) MRN from the Integrated Data Repository (IDR) for 75 randomly selected patients from both control and intervention practices in Gainesville and Jacksonville, which will be reviewed for 1) adherence to the 6As (through whichever number of steps are applicable for that patient) inclusive of tobacco and nicotine product use and 2) parental screening for tobacco use. Specifically, the IDR will be asked to select MRNs from 75 records consecutively from well care visits from participating providers for patients 11 through 17 years of age from the 6 months prior to the start of the study until they reach 75 records. OneFlorida has a medical record review team with certified medical record coders. The medical record review team will measure compliance with the 6As and parental screening using the review tool. At the end of the intervention period, we will request the medical records for those patients participating in the intervention. We will request MRNs from the IDR for control group practices and review 75 consecutive medical records for patients ages 11 through 17 years seen during the 6 month study period.

[name] will train the medical record reviewers for the Gainesville and Jacksonville sites. Interrater reliability will be established and training will continue until there is 98% agreement between reviewers. During the record review process, [name] will be available to the reviewers to respond to questions. If there is not 98% agreement among the medical record reviewer findings, the medical record reviewers will undergo additional training from [name]..

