**Figure 2. Study Overview and Intervention**

Intervention Practices N=2	Control Practices N=2
Baseline	Baseline

 
• Complete Clinician and Practice Surveys
 
• Usual Care Documentation
 
• Medical Record Reviews
 
	
 
• Complete clinician and Practice Surveys
 
• Usual Care Documentation
 
• Medical Record Reviews
 

The Intervention	Usual Care

 
• Protocol Adaptation
 
• ResearchACTS –TPNQ,6As Prompts, Parent Screening & Registry
 
• Practice Facilitators
 
• MOC support
 
	
 
• Tobacco and Nicotine Screening & Counseling
 

Outcomes	Outcomes

 
• Practice Compliance
 
• Child Reported Visit Outcomes
 
• Clinician and Practice Changes
 
	
 
• Practice Compliance
 
• Child Reported Visit Outcomes
 
• Clinicians and Practice Changes
 

	Post Study
	
 
• Support for MOC
 

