### 6.2.5 Analysis Plan

Intervention effect on clinician adherence to the 6As: The primary outcome is clinician adherence to the 6As inclusive of tobacco and nicotine product use as collected in the medical records. During both the baseline and follow-up periods, we will request and review medical records to identify the following primary outcome measures: discussion of patient’s tobacco use, advice to quit, and discussion of parent’s tobacco use. Since this is a pre-post design with one intervention group and one control group, we will perform ANCOVA-type analyses assuming that the patients and providers are independent of each other. For each outcome, we will fit a logistic regression model in which the dependent variable is the post-intervention measure of the outcome. The main independent variables will be the pre-intervention measure of the outcome, group (binary: intervention vs. control), and pre-intervention measure by group interaction. In all models, we will also control for age, gender, and race, and clinic (multi-nominal: clinics 1-4). The model building process will follow guidelines provided by Hosmer and Lemeshow.

Intervention effect on practice characteristics: Practice characteristic data will be measured from the Change Process Capability Questionnaire and the Adaptive Reserve Questionnaire (Appendix B). We will collect the practice characteristic data twice, once at baseline and once at 9 months. Therefore, we will fit ANCOVA models for data analysis, assuming the practices are independent of each other. The characteristics include meeting frequency, clinician/staff performance evaluation, and planned communication. The primary predictor of interest is group (intervention vs. control). The model building process will follow guidelines provide by Muller and Fetterman. We will perform residual analysis to check the normality assumption of the models. We will perform box-cox transformation if there is a violation of the normality assumption.

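### Randomisation of two of four practices is not restricted by city as written; if it is unrestricted, 2 of 6 allocations (33%) make arm and city the same contrast, and city-specific change cannot be separated from the intervention effect

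*Combined protocol and SAP*

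**What the plan says.** Section 6.2.1 contains the whole allocation rule. The sample is four practices chosen for convenience, of which "Two will be randomly assigned to receive the intervention and two will serve as the comparison groups". The next sentence adds that "Two of the practices will be located at UF Health in Gainesville and two will be located at UF Health in Jacksonville". Figure 2 confirms the arm sizes ("Intervention Practices N=2", and likewise two controls). Neither section 6.2.1 nor any other part of the supplied document says that the draw is stratified, matched or otherwise restricted by city.

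The nearest thing to such a statement is in section 6.2.3, item E, where baseline records are requested for "75 randomly selected patients from both control and intervention practices in Gainesville and Jacksonville". That sentence describes how charts are sampled. It does not say how practices are allocated.

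The primary analysis in section 6.2.5 is a logistic regression in which "the dependent variable is the post-intervention measure of the outcome". Its main predictors are the pre-intervention measure, "group (binary: intervention vs. control), and pre-intervention measure by group interaction". Age, gender, race and a four-level clinic factor are also included. There is no city term, no period term and no arm-by-period term.

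**The concern.** With two practices against two, chance cannot be relied on to balance city. If both intervention practices fall in one city, the comparison of arms is also the comparison of Gainesville with Jacksonville. A fixed difference between the cities could still be taken out by comparing each practice with its own baseline. A difference in how the cities change over the study could not. Anything that alters charting or tobacco counselling in one city during those months would be read as an intervention effect, or would hide one.

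The problem is set at the moment of allocation. After a same-city draw, no covariate or change of model can separate the two explanations. Aim 2 is to gather pilot data on effectiveness, so a one-in-three chance of an estimate that cannot be told apart from a city effect is a real loss to that aim.

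**Working it through.** The plan states no allocation probability, so there is no figure of its own to reproduce. The check is a count of allocations followed by a test of which effects can be estimated in each.

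**Inputs.** Four practices, two per arm and two per city (section 6.2.1, Figure 2). Call them G1, G2 (Gainesville) and J1, J2 (Jacksonville). All 2:2 allocations are taken as equally likely, which is the assumption of unrestricted randomisation.

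**Count.** The number of allocations is C(4,2) = 6. Let d be the Jacksonville change minus the Gainesville change in the documentation rate that would occur without the intervention. The error it puts into the arm difference in change (intervention minus control) is:

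| Intervention | Control | Arm and city | Error from city change |
|---|---|---|---|
| G1, G2 | J1, J2 | aliased | −d |
| G1, J1 | G2, J2 | uncorrelated | 0 |
| G1, J2 | G2, J1 | uncorrelated | 0 |
| G2, J1 | G1, J2 | uncorrelated | 0 |
| G2, J2 | G1, J1 | uncorrelated | 0 |
| J1, J2 | G1, G2 | aliased | +d |

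P(aliased) = 2/6 = 33%. With one intervention practice drawn within each city there are 2 × 2 = 4 allocations, the middle four rows, and 0 of 4 are aliased.

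**Estimability.** The rank of the design matrix shows whether the arm effect can be separated from the other terms:

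- Post-period model with arm and city: estimable in 4 of 6 allocations.
- Clinic, period and arm-by-period (a difference-in-change model): 6 of 6. This removes stable city differences but assumes that both cities change alike.
- The same model plus city-by-period: 4 of 6 unrestricted, 4 of 4 paired. In the two aliased draws the matrix has rank 6 for 7 columns; in the other four it has rank 7 of 7.
- Post-period model with arm and the four-level clinic factor, as in section 6.2.5: 0 of 6. The arm column is a sum of clinic columns (rank 4 for 5 columns). This is a separate defect and is the same under any allocation.

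**Size.** The documents give no value for d, so a range is assumed. The mean error over the six draws is (−d + d)/6 = 0. The root-mean-square error is √[(d² + d²)/6] = d√(2/6) = 0.577d:

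- d = 5 points: 0.577 × 5 = 2.9 points
- d = 10 points: 0.577 × 10 = 5.8 points
- d = 15 points: 0.577 × 15 = 8.7 points

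Under pairing the city component of the error is 0 in every draw. These figures average over all six draws; in an aliased draw the error is the full d.

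**The case against.** The documents never say that allocation was unrestricted. Two practices per city and two per arm fit a one-per-city-per-arm plan, and the sampling sentence in section 6.2.3 can be read as placing both arms in each city. This stands in part: pairing may have been intended. But that sentence is equally true if one city holds both intervention practices and the other both controls, so it cannot stand in for an allocation rule.

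The document also gives no evidence that the cities would change differently. Both are UF Health locations, and the chart review uses one team with common training, where "training will continue until there is 98% agreement between reviewers". This stands as a limit on size. It makes reviewer differences only a possible contributor, and d remains an assumption. It does not bear on real differences in how practice or charting changes in each city.

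Unrestricted randomisation has zero mean error from city, as the table shows. That is true of the procedure, but only one draw will be made, and in two of the six the error is the whole of d.

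Pairing has costs, and it does not rescue the planned model, whose clinic term aliases arm under every allocation. Both statements are correct. The model needs its own correction, but that correction cannot repair a same-city draw.

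Finally, this is a four-practice pilot that cannot support practice-level inference at 0.05 under either scheme. That makes an interpretable estimate the main product, and a same-city draw would damage exactly that.

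**Conclusion.** The concern holds. As written, section 6.2.1 permits a draw in which arm and city are the same contrast, with probability 2/6 = 33% if allocation is unrestricted, against 0/4 if it is paired by city. In such a draw, city-specific change over time cannot be separated from the intervention effect by any analysis. The model in section 6.2.5 takes the follow-up measure as its outcome and has no arm-by-period term, so it does not clearly remove even a stable city difference.

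The probability is exact, given equally likely 2:2 allocations. The size of the resulting error depends on d, which the documents do not give; for an assumed 5 to 15 points the root-mean-square error is 2.9 to 8.7 points. The conclusion covers the city component only. Differences in change between individual practices remain entangled with arm whichever four-practice allocation is used. This should be corrected, but it is a conditional risk and not a demonstrated bias.

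**What to change.** In section 6.2.1, state that within each city one practice is randomised to intervention and the other to control. In section 6.2.5, report the two within-city differences in change: follow-up minus baseline, intervention minus control, once for Gainesville and once for Jacksonville.

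If practices have already been assigned, state the method that was used and which arm each city's practices are in. If both intervention practices are in one city, say plainly that city-specific change cannot be separated from the intervention effect.

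The cost in text is one sentence in each section. The statistical cost is small but not nil:

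- Allocations fall from 6 to 4, so the smallest two-sided randomisation p-value rises from 2/6 = 0.33 to 2/4 = 0.50. Neither can reach 0.05.
- Fitting city in a practice-level change model leaves 4 − 3 = 1 residual degree of freedom instead of 4 − 2 = 2.
- Both arms would be present in each city in 4 of 4 draws instead of 4 of 6. Any clinicians shared between same-city practices should therefore be checked; the documents do not say whether there are any.

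The four-level clinic term in section 6.2.5 must be corrected separately, because it aliases the arm main effect under every allocation.

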### 6.2.2 Sample

In Florida, only 4.3 percent of children ages 11 to 17 are current cigarette smokers. However, e-cigarette use is increasing from 5 percent of Florida high school students in 2013 to 11 percent in 2014. While the percentage of adolescents at risk to begin smoking is not known, studies have identified maternal smoking, trying tobacco, alcohol or marijuana by 8th grade, and endorsement of sensation seeking behavior as risk factors for tobacco and related product use. Children should be screened for these risks.

We will screen all youth, ages 11 through 17 years, in the practice for current tobacco use and risk behaviors associated with cigarette and nicotine product use with the goal of reaching 20 children per practice who are current tobacco users who could receive at least one or more of Steps 3 through 6 (advise, assess, assist, arrange). To achieve 20 patients per practice who reach the “advise” and “assess” stages, if the practice had the average percentage of children using e-cigarettes, approximately 218 patients would need to be screened. The number screened to reach the “advise” and “assess” stages is based on the e-cigarette use and not the traditional cigarette use.

Intervention practices will be asked to screen patients for tobacco and nicotine product use (using the anticipate and ask components of the 6As) by having youth complete a tobacco and nicotine use screening tool until the practice has identified and completed at least the “advise” and “assess” intervention on 20 tobacco/nicotine users. Parental consent and adolescent assent will be electronically obtained using ResearchActs software. In addition, practices will be asked to implement a short parental screening tool for tobacco use. The parent and child will respond to the surveys separately. After the child completes the survey s/he will be offered a \$5 electronic Amazon gift card.

Practices will be asked to identify a location in the waiting room or an exam room where the screening tool can be completed without the parent present. Completing the tool is expected to take 10 minutes of the youth's time and 10 minutes of the parent's time, inclusive of the time to complete the informed consent. We estimate practices will need to participate in the project for approximately 6 months. This time period includes baseline and follow-up data collection, study implementation, and participant accrual. The 6-month time period is also necessary for those practices who wish to use the project for participation in their Maintenance of Certification (MOC) requirements.

The total duration of study participation for the practices is estimated to be 10 months. This includes a 3-month start up period, a 6-month intervention (or control) time period and a 1-month follow-up. The 6-month intervention period is necessary for those practices who want to use the study participation to assist them in meeting their MOC requirements. For practices not participating in the MOC Program, the intervention period is finished when 20 patients complete at least the “advise” and “assess” components.

Practices can make some modifications to the intervention to fit with their workflow. For example, some practices have nursing staff screen for tobacco/nicotine use and make recommendations about cessation strategies. Other practices have physicians provide the screening and counseling. Practices can make adaptations regarding who administers the 6As but they must follow the 6A intervention. Any type of primary care visit can be used to conduct the 6As.

The duration of the study participation for patients is variable. For those who do not smoke/use nicotine products or who smoke/use nicotine products but do not want to quit, the duration of the study is the baseline data collection (5 to 10 minutes for the youth and 5 to 10 minutes for the parent, inclusive of the informed consent), clinician screening and advising (2 to 5 minutes for the child and 2 to 5 minutes for the parent), and the follow-up telephone survey administered through the UF Survey Research Center (10 minutes) for a total estimated participation time of approximately 25 to 30 minutes. Adolescent participants will be offered another \$5 electronic Amazon gift card after completion of the follow-up telephone survey. For patients who smoke/use nicotine products and want to quit, their participation is an estimated 35 minutes for baseline and follow-up telephone survey data collection and provider discussion during the primary care visit. Practices can customize who conducts the screening and advising. For example, some practices assign that role to the nursing staff. In other practices, the clinician seeing the patient for the visit provides this screening and counseling himself or herself.

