## Appendix C. Youth Tobacco and Nicotine Product Questionnaire (Y-TNPQ)

### Section 1. Screening Questions:

1. Have you ever used any of the following tobacco products, even one or two times? Check all that apply.
  - a. Cigarettes
  - b. E-cigarettes, such as Blu or Smoking Everywhere
  - c. Cigars, cigarillos, or filtered cigars
  - d. Hookah, shisha, or waterpipe
  - e. Smokeless tobacco, such as snus, pouches, snuff, dip, or chewing tobacco
  - f. I have never used tobacco products

- If Q1=a **[go to Q2]**
- If Q1=b **[go to Q3]**
- If Q1=c **[go to Q4]**
- If Q1=d **[go to Q5]**
- If Q1=e **[go to Q6]**
- If Q1= f **then never established tobacco use, [assess susceptibility using the items S1-S3]**

2. Do you currently use any tobacco products such as cigarettes, e-cigarettes, cigars, cigarillos or filtered cigars, hookah, shisha or waterpipe, snus pouches, snuff, dip, or chewing tobacco every day, some days, or not at all?
  - a. Everyday
  - b. Some days
  - c. Not at all

S1. Do you think you might try a cigarette or other tobacco product?

- a. Definitely yes
- b. Probably yes
- c. Probably not
- d. Definitely not

S2. If one of your best friends were to offer you a cigarette or other tobacco product, would you use it?

- a. Definitely yes
- b. Probably yes
- c. Probably not
- d. Definitely not

S3. Do you think you might be smoking cigarettes or using tobacco 1 year from now?

- a. Definitely yes
- b. Probably yes
- c. Probably not
- d. Definitely not

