**Best Practice:**

1. Documentation that youth was asked about current use of:
  - a. Cigarettes
  - b. Cigars/Cigarillos
  - c. E-cigarettes
  - d. Hookah
  - e. Smokeless tobacco products
2. If youth smokes or uses nicotine products, was youth asked about amount used (e.g., just a puff, 5 cigarettes a day and so on)?
3. If youth smokes or uses nicotine products, was youth asked about how often used (e.g., daily, monthly and so on)?
4. Was youth asked if he/she anticipated using cigarettes or nicotine products in the future?
5. Was youth advised to not use: Cigarettes, Cigars/cigarillos, E-cigarettes, Hookah, or Smokeless tobacco products
6. For those who smoke or use tobacco products was youth asked if they were ready to quit?
7. For those who were ready to quit, was a referral made?
8. Regardless of readiness to quit, were youth given or told about resources that are available to learn more about the hazards of tobacco and nicotine use?
9. Regardless of readiness to quit, was youth given/told about resources to quit should s/he decide to do so?
10. Was parental tobacco use assessed?
11. Were parent(s) asked about?
  - a. Smoke free home
  - b. smoke free car
  - c. If anyone caring for the child smokes
12. If parent(s) smokes or uses nicotine products in the home or car, was s/he advised to quit smoking?
13. If parent(s) smokes, was s/he referred to smoking cessation programs?
14. If parent(s) smokes was s/he told about educational resources on the influence of parental smoking on the child/youth?

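### The youth tool assigns its Anticipate questions to never-users only, and its printed skips bypass the current-use question for youths who have used only non-cigarette products

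*Combined protocol and SAP*

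**What the plan says.** Section 4 (Background) defines the first of the 6As, Anticipate, as concerning future use, with no restriction to youths who have never used a product. Section 6.2.2 makes the youth questionnaire the vehicle for the first two steps: practices screen "using the anticipate and ask components of the 6As) by having youth complete a tobacco and nicotine use screening tool". The same section lists risk factors for later use, among them having tried tobacco, alcohol or marijuana by 8th grade, and adds "Children should be screened for these risks".

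Appendix C opens with "Have you ever used any of the following tobacco products, even one or two times", offering five product groups (a to e) and never used (f). Only answer f carries the instruction "assess susceptibility using the items S1-S3". S1-S3 ask whether the youth might try a product, would accept one from a friend, and might be using a year from now. Q2 asks about current use, with *Not at all* as one answer, and no instruction is attached to that answer.

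In the medical record review (Appendix E), item 4 asks "Was youth asked if he/she anticipated using cigarettes or nicotine products in the future". It has no condition on use status, whereas items 2, 3 and 6 are limited to youths who smoke or use.

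**The concern.** The protocol gives the tool the job of delivering Anticipate, but the tool's printed routing gives the future-use items to one group only. A youth who took a puff last year and has not used since leaves the never-used branch at Q1 and is not directed to S1-S3. As a non-user, this youth also falls outside the readiness-to-quit item (Appendix E, item 6). Yet this youth may belong to one of the risk groups that section 6.2.2 cites.

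Aim 1 is to develop and deploy this tool, so what it asks, and of whom, is part of the intervention. Two things are at stake. The clinician may see no future-use answer for past triers. And the record review scores item 4 without regard to use status, while the tool asks about future use in a subset, so a gap in the tool could be read as a gap in clinician practice.

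Tracing the routing exposes a second fault. Some ever-users are never sent to the current-use question at all, so the tool cannot tell whether they count towards the 20 current users sought per practice.

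**Working it through.** This is a check of the documents rather than a calculation. The printed skips in Appendix C, set against the items that carry those numbers, give:

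| Q1 answer | Sent to | Item found there | Current use (Q2) assigned? | S1-S3 assigned? |
|---|---|---|---|---|
| a. Cigarettes | Q2 | Current use of any product | Yes | No instruction |
| b. E-cigarettes | Q3 | Household use | No | No |
| c. Cigars | Q4 | Age | No | No |
| d. Hookah | Q5 | Sex | No | No |
| e. Smokeless | Q6 | Grade | No | No |
| f. Never used | S1-S3, then Q7 | Future use, then Hispanic origin | Not needed | Yes |

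Four things follow.

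1. One of six answers leads to S1-S3. No instruction takes an ever-user there, whatever the answer to Q2. Current users are not sent there either.
2. A youth who ticks only b, c, d or e is not asked Q2. Such a youth cannot be classed as a current or past user from the tool. Section 6.2.2 states that the number to screen is based on e-cigarette use, so this is the group on which the target depends.
3. Never-users go from S1-S3 to Q7 and so miss household use, age, sex and grade (Q3 to Q6). Youths who answer c, d or e miss some of these items too.
4. Q1 allows several answers, so a youth who ticks two products is given two destinations.

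S1-S3 are printed directly below Q2 with no skip between them. A cigarette ever-user who simply reads on could therefore reach them, but that is layout, not an instruction.

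**Number affected by the first gap.** The documents give no share of youths who have tried a product but do not use now. The shares below are assumptions for illustration. The numbers screened per intervention practice are those stated in section 6.2.2 (218) and section 6.2.3 C (190).

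Youths assigned no future-use item = assumed share × number screened:

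| Assumed share | of 190 | of 218 |
|---|---|---|
| 5% | 0.05 × 190 = 9.5 | 0.05 × 218 = 10.9 |
| 10% | 0.10 × 190 = 19.0 | 0.10 × 218 = 21.8 |
| 20% | 0.20 × 190 = 38.0 | 0.20 × 218 = 43.6 |

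That is about 10 to 44 past triers per practice. The plan states no figure of its own to reproduce here.

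**The case against.** The strongest reply is that the tool is not the only route to Anticipate. Under section 6.2.3 C the clinician reviews the answers in ResearchACTS and is prompted through the 6As. Section 6.2.2 obliges practices to follow the 6As whoever administers them, and allows 2 to 5 minutes of clinician time with the child even for non-users. Aim 1 trains clinicians and staff. A reader might infer from Appendix C that past triers receive no Anticipate step at all. The documents do not support that. They do not show the prompts for this group, and the prompts depend on the child's answers, so delivery by the clinician is neither assured nor excluded.

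A reader might also infer that the item 4 rate must fall by the share of past triers, and that the effect on Anticipate is understated by that much. This does not follow either. Item 4 is scored from the medical record, and nothing says that answers held in ResearchACTS count as chart documentation. Current users are not routed to S1-S3 either, so the youths without a tool question are all ever-users, not only past triers. Section 6.2.5 names three primary measures: discussion of the patient's use, advice to quit, and discussion of the parent's use. Anticipate is not among them.

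Third, the skip pattern is visibly out of step with the item numbers and may not reflect what was programmed. That is fair, but the printed appendix is all the documents show, and it needs repair in any case.

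Finally, the tool has no item on alcohol, marijuana or sensation seeking, and section 6.1 says patient factors such as "impulsivity, and other factors are integral to tobacco and nicotine product cessation interventions and will be incorporated into future research". A reader might see a contradiction with section 6.2.2. It is at most loose wording: section 6.1 concerns factors in cessation interventions, Q1 does record past trial, and household and parental use are asked in Appendices C and D.

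**Conclusion.** The point holds as a mismatch between section 6.2.2 and Appendix C. By its printed routing, the tool that is meant to carry out Anticipate assigns the future-use items to never-users only. Youths who have tried a product but do not use now are assigned none, and whether clinicians make up for this cannot be told from the documents. Those who report only non-cigarette products are also not asked about current use, which leaves the tool unable to identify the e-cigarette users on whom the screening target rests.

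The first gap would touch about 10 to 44 youths per intervention practice if 5% to 20% of those screened were past triers. That range is only as good as the assumed share. This group overlaps with the risk group in section 6.2.2 (trying by 8th grade) but is not identical to it. No bias in the primary measures is claimed. This is a modest design repair, worth making because developing the tool is itself an aim of the pilot.

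**What to change.** In Appendix C:
- send every Q1 answer from a to e to Q2, including when several are ticked;
- send Q1=f and Q2=*Not at all* to S1-S3;
- send all youths on to the household-use and demographic items;
- name e-cigarettes and other nicotine products in S1-S3, to match chart item 4.

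The Q2 repair has to come with the S1-S3 change, because the new route depends on an answer that the printed skips do not collect from answers b to e.

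In Appendix E, state whether item 4 applies to all youths or only to those who are not current users, so that its denominator matches the group the tool asks. In section 6.2.2, say what the tool measures under risk behaviors: past trial, susceptibility and household use.

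The cost is a change to the skip logic in ResearchACTS, up to three short existing questions for past triers, Q2 for youths who now bypass it, the household and demographic items for those now sent past them, and a minor amendment.
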